Appendix D Definition of Cardiovascular Disease Risk Categories

- **Very high CV risk** is defined as a history of documented CHD, ischemic stroke, transient ischemic attack, carotid artery occlusion >50% without symptoms, carotid endarterectomy or carotid artery stent procedure, peripheral arterial disease, abdominal aortic aneurysm, renal artery stenosis, renal artery stent procedure, type 1 or type 2 diabetes mellitus with target organ damage.
 - A history of documented CHD includes 1 or more of the following:
 - Acute myocardial infarction.
 - Silent myocardial infarction.
 - Unstable angina.
 - Coronary revascularization procedure (eg, percutaneous coronary intervention or coronary artery bypass graft surgery).
 - Clinically significant CHD diagnosed by invasive or non-invasive testing (such as coronary angiography, stress test using treadmill, stress echocardiography or nuclear imaging).
- **High CV risk** is defined as a calculated 10-year fatal CVD risk SCORE $\geq 5\%$ (1), moderate chronic kidney disease, type 1 or type 2 diabetes mellitus without target organ damage, or heFH.
- **Moderate CV risk** is defined as a calculated 10-year fatal CVD risk SCORE ≥ 1 and $< 5\%$ (1).

Appendix E General guidance for the follow-up of ALT increase by Sanofi

Appendix F Procedure for collection, handling, storage and shipment of SAR236533, pharmacokinetic, and anti-SAR236553 antibody samples

1. SAMPLING SUPPLIES DESCRIPTION

Serum SAR236553 samples	Collection material: 5mL red-top vacutainer tubes (containing no additives or anti-coagulant, B-D Cat #367814; Vacutainer 5mL tubes) for serum
	
Storage tube:
 
Aliquot approximately equal volumes of serum into TWO separate 1.8 mL plastic 2D barcoded cryovials, one for the primary aliquot and one for the duplicate aliquot. Do not exceed 1.0 mL of serum into each cryovial. Use one of the approved cryovials listed below.
 
 • Nunc Item # 374502 • VWR: Catalog # 89233-708 • ThermoFisher/USA Scientific: Catalog # 12590007
Serum Anti-SAR236553 antibody (ADA) samples	Collection material: 5mL red-top vacutainer tubes (containing no additives or anti-coagulant, B-D Cat #367814; Vacutainer 5mL tubes) for serum
	
Storage tube:
 
Aliquot approximately equal volumes of serum into TWO separate 1.8 mL plastic 2D barcoded cryovials, one for the primary aliquot and one for the duplicate aliquot. Do not exceed 1.0 mL of serum into each cryovial. Use one of the approved cryovials listed below.
 
 • Nunc Item# 374502 • VWR: Catalog # 89233-708 • ThermoFisher/USA Scientific: Catalog # 12590007
Miscellaneous	Refrigerated centrifuge Collection material provided by Contract Research Organization (CRO)
	Specimen storage labels for SAR236553 provided by: CRO Specimen storage labels for anti- SAR236553 provided by: CRO Specimen storage tube labels for pharmacogenetic specimens provided by Covance, Indianapolis, IN
	Styrofoam shippers with boxes, shipping labels, Ziplock storage bag, and any other necessary packaging supplies in order to comply with IATA Dangerous Goods Regulations, Packing Instructions 650 for shipment below 0°C.

2. SERUM SAR236553 AND ANTI-SAR236553 ANTIBODY (ADA) SAMPLES

2.1 Collection/Handling/Processing of Samples

Collection schedule

Per protocol

PK Serum Sample Collection and Preparation

- At intervals stated in the clinical study protocol, whole blood from subjects will be collected in 5-mL red-top vacutainer tubes (US B-D Cat #367814, European B-D Cat #369032) containing clot activator and no additional additives or anti-coagulant for **PK SERUM** sample preparation.
- Collect 5 mL blood directly into 5-mL red-top vacutainer tube and invert 5 times.
- Allow blood to clot for 30 minutes.
- Centrifuge at approximately 1200 x g for 15 minutes to separate clot from serum.
- Within 30 minutes after centrifugation, draw off serum very slowly with transfer pipette, approaching no closer than 0.5 cm of the buffy coat and taking great care not to disturb the buffy coat (any contamination may invalidate the assay).
- All cryovials must be properly labeled with labels provided by CRO as per the laboratory manual.
- Aliquot approximately equal volumes of serum into **TWO** separate 1.8-mL plastic 2D barcoded cryovials, one for the primary aliquot and one for the duplicate aliquot. Do not exceed 1 mL of serum into each cryovial. Use one of the approved cryovials listed below.
 - Nunc Item # 374502
 - VWR: Catalog # 89233-708
 - ThermoFisher/USA Scientific: Catalog # 12590007
- Freeze all cryovials immediately. All serum samples must be stored in a -20° C or colder freezer that does **NOT** auto-defrost until the next earliest shipment. For long-term storage, all serum samples should be stored in a -80° C freezer.
 - **Note: If the site does not have a -20°C or colder freezer that does NOT auto-defrost, ship the serum samples on dry ice on the day of collection to CRO.**
- Sites must ship the primary aliquot in a separate shipment from the duplicate aliquot.

ADA Serum Sample Collection and Preparation

- At intervals stated in the clinical study protocol, whole blood from subjects will be collected in 5-mL red-top vacutainer tubes (US BD Cat #367814, European B-D Cat #369032) containing clot activator and no additional additives or anti-coagulant for **ADA SERUM** sample preparation.
- Collect 5 mL blood directly into 5-mL red-top vacutainer tube and invert 5 times.
- Allow blood to clot for 30 minutes.
- Centrifuge at approximately 1200 x g for 15 minutes to separate clot from serum.
- Within 30 minutes after centrifugation, draw off serum very slowly with transfer pipette, approaching no closer than 0.5 cm of the buffy coat and taking great care not to disturb the buffy coat (any contamination may invalidate the assay).
- All cryovials must be properly labeled, with labels provided by CRO as per the laboratory manual.
- Aliquot approximately equal volumes of serum into **TWO** separate 1.8-mL plastic 2D barcoded cryovials, one for the primary aliquot and one for the duplicate aliquot. Do not exceed 1 mL of serum into each cryovial. Use one of the approved cryovials listed below.
 - Nunc Item# 374502
 - VWR: Catalog # 89233-708
 - ThermoFisher/USA Scientific: Catalog # 12590007
- Freeze all cryovials immediately. All serum samples must be stored in a -20° C or colder freezer that does **NOT** auto-defrost until the next earliest shipment. For long-term storage, all serum samples should be stored in a -80° C freezer.
 - **Note: If the site does not have a -20°C or colder freezer that does NOT auto-defrost, ship the serum samples on dry ice on the day of collection to PPD Central Labs.**
- Sites must ship the primary aliquots in a separate shipment from the duplicate aliquots.

2.2 Labeling of specimens

Additional instructions will be provided by the central lab vendor and/or the Sponsor.

Appendix G Local injection site reactions assessment

Reaction to Injectable Product	Mild (Grade 1)	Moderate (Grade 2)	Severe (Grade 3)	Very Severe (Grade 4)
Pain	Does not interfere with activity	Interferes with activity or repeated use of non-narcotic pain reliever	Prevents daily activity or repeated use of narcotic pain reliever	Emergency Room (ER) visit or hospitalization
Tenderness	Mild pain to touch	Pain with movement	Significant pain at rest	ER visit or hospitalization
Erythema / Redness *	2.5 – 5 cm	5.1 – 10 cm	>10 cm	Necrosis or exfoliative dermatitis
Swelling **	2.5 – 5 cm and does not interfere with activity	5.1 – 10 cm or interferes with activity	> 10 cm or prevents daily activity	Necrosis
Itching	Does not interfere with activity	Interferes with activity or repeated use of topical or systemic treatment	Prevents daily activity or leads to other significant dermatologic conditions (such as infection, scarring, etc.)	Emergency Room (ER) visit or hospitalization
Other (Please specify)***	No modification of daily activities and/or does not require symptomatic treatment.	Hinders normal daily activities and/or requires symptomatic treatment.	Prevents daily activities and requires symptomatic treatment.	Emergency Room (ER) visit or hospitalization

* In addition to grading the measured local reaction at the greatest single diameter, the measurement should be recorded as a continuous variable.

** Swelling should be evaluated and graded using the functional scale as well as the actual measurement.

*** Please specify the other signs or symptoms (for example, hematoma, discoloration, re-activation, etc.).

ADAPTED from the toxicity grading scale table from the FDA Draft Guidance for Industry: Toxicity Grading Scale for Healthy Adult and Adolescent Volunteers Enrolled in Preventive Vaccine Clinical Trials April 2005

Appendix H Clinical diagnosis of heterozygous familial hypercholesterolemia (heFH)

WHO Criteria (Dutch Lipid Network clinical criteria) for diagnosis of Heterozygous Familial Hypercholesterolemia (heFH)

Diagnostic Scoring for Heterozygous Familial Hypercholesterolemia			
Family history			
a	First degree relative with known premature (men <55 yrs, women <60 yrs) coronary and vascular disease.		1
b	First degree relative with known LDL-cholesterol >95th percentile for age and sex.		
and/or			
a	First degree relative with tendon xanthomata and/or arcus cornealis.		2
b	Children below 18 yrs. with LDL-cholesterol >95th percentile for age and sex.		
Clinical history			
a	Patient has premature (men <55 yrs, women <60 yrs) coronary artery disease		2
b	Patient has premature (men <55 yrs, women <60 yrs) cerebral or peripheral vascular disease.		1
Physical examination			
a	Tendon xanthomata		6
b	Arcus cornealis below the age of 45 yrs.		4
Laboratory analysis			
		mmol/L	mg/dL
a	LDL-cholesterol	>8.5	>330
b	LDL-cholesterol	6.5-8.4	250-329
c	LDL-cholesterol	5.0-6.4	190-249
d	LDL-cholesterol	4.0-4.9	155-189
(HDL-cholesterol and triglycerides are normal)			
DNA-analysis			
a	Functional mutation low-density lipoprotein receptor gene present		8
Diagnosis of heFH is:			
	Certain When		>8 points
	Probable When		6-8 points
	Possible When		3-5 points

Simon Broome Register Diagnostic Criteria for Heterozygous Familial Hypercholesterolemia

Definite familial hypercholesterolemia is defined as:

- Total-C >6.7 mmol/L (260 mg/dL) or LDL cholesterol above 4.0 mmol/L (155 mg/dL) in a child <16 years or Total-C >7.5 mmol/L (290 mg/dL) or LDL cholesterol above 4.9 mmol/L (190 mg/dL) in an adult. (Levels either pre-treatment or highest on treatment).

PLUS

- Tendon xanthomas in patient, or in 1st degree relative (parent, sibling, child), or in 2nd degree relative (grandparent, uncle, aunt).

OR

- DNA-based evidence of an LDL receptor mutation or familial defective apo B-100.

Possible familial hypercholesterolemia is defined as:

- Total-C >6.7 mmol/L (260 mg/dL) or LDL cholesterol above 4.0 mmol/L (155 mg/dL) in a child <16 years or Total-C >7.5 mmol/L (290 mg/dL) or LDL cholesterol above 4.9 mmol/L (190 mg/dL) in an adult. (Levels either pre-treatment or highest on treatment).

And at least one of the following:

- Family history of MI below 50 years of age in 2nd degree relative or below 60 years of age in 1st degree relative.

1 OVERVIEW AND INVESTIGATIONAL PLAN

This statistical analysis plan (SAP) provides a comprehensive and detailed description of strategy and statistical technique to be used for the clinical study reports of MSC14864 study.

The overall goal of this study, MSC14864, is to assess the usability of SYDNEY (New device).

1.1 STUDY DESIGN AND RANDOMIZATION

This is a multicenter, randomized, open-label, 16-week study conducted in the USA, with 2 parallel arms (parallel-arm period) for the first 4 weeks, and then only one arm (single-arm period) for the subsequent weeks until Week 16.

Eligible patients will be randomly allocated to receive alirocumab 300 mg Q4W, self-administered using either the approved AI or the new investigational AI (SYDNEY) device for the first injection on Day 1. This injection will be performed at the clinical site under supervision and guidance by staff from the site.

Subsequently, all patients will receive alirocumab 300 mg Q4W self-administered using only SYDNEY device for the injections on Week 4 (Day 29), Week 8 (Day 57) and Week 12 (Day 85) respectively.

1.2 OBJECTIVES

1.2.1 Primary objective

To collect 12 weeks of real-use (usability) data assessing the robustness and user interaction of SYDNEY, in unsupervised settings on Weeks 4, 8, and 12.

1.2.2 Secondary objectives

Device related:

- To collect real-use (usability) data assessing the robustness and user interaction of SYDNEY and the current AI 1 mL alirocumab auto-injector device in supervised settings on Week 0 (Day 1).

Pharmacokinetics:

- To compare alirocumab pharmacokinetics 300 mg Q4W administered using SYDNEY and the current AI, from baseline until Week 4.
- To evaluate alirocumab PK 300 mg Q4W administered using SYDNEY, until Week 16.

Anti-drug antibodies:

- To evaluate the development of ADA.

Pharmacodynamics:

- To compare the percent and absolute change in LDL-C from baseline to Week 4 using SYDNEY and the current AI.
- To evaluate the percent and absolute change in LDL-C from baseline to Weeks 8, 12 and 16, using SYDNEY.

Safety:

- To evaluate the safety and tolerability of alirocumab 300 mg Q4W, using both Auto Injector Devices.

1.3 DETERMINATION OF SAMPLE SIZE

[figure not shown]
No formal sample size was calculated, the sample size is based on empirical considerations.

Considering a drop-out rate of 10% it is planned to randomize 66 patients overall (33 in each group) in order to ensure 60 evaluable patients overall (30 in each group) resulting in 180 unsupervised planned injections using SYDNEY, including the 2nd, 3rd and 4th unsupervised injections with SYDNEY for patients randomized in the approved AI group who will switch to SYDNEY group just before the second injection.

Expecting a maximum of 3 observed PTC over the 180 injections (observed PTC rate of 1.67%) with SYDNEY, the upper bound of the 2-sided 95% CI calculated with the Wilson score method will be no higher than 5.2%.

1.4 STUDY PLAN

The following figure presents the graphical study design:

1.5 MODIFICATIONS TO THE STATISTICAL SECTION OF THE PROTOCOL

Not applicable.

1.6 STATISTICAL MODIFICATIONS MADE IN THE STATISTICAL ANALYSIS PLAN

Not applicable.

2 STATISTICAL AND ANALYTICAL PROCEDURES

Analyses will be performed in each study phase (parallel arms phase and the single arm phase) separately unless otherwise specified. The results will be presented by treatment arm (SYDNEY, and approved AI) for the parallel arm phase and overall for the single arm phase.

2.1 ANALYSIS ENDPOINTS

2.1.1 Demographic and baseline characteristics

For both study phases, the baseline value is defined as the last available value prior to the first dose of study medication planned at Day 1.

All baseline safety and pharmacodynamics parameters (apart from those listed below) will be presented along with the on-treatment summary statistics in the safety and pharmacodynamics sections ([Section 2.4.4.2.5](#) and [Section 2.4.4.2.4](#)).

Demographic characteristics

Demographic variables are:

- Gender (Male, Female)
- Race (White, Black or African American, Asian, American Indian or Alaska Native, Native Hawaiian or other Pacific Island)
- Ethnicity (Hispanic or Latino, Not Hispanic or Latino)
- Age in years (quantitative and qualitative variable: <65, ≥65 to <75, and ≥75 years)

Medical or surgical history

Medical or surgical history includes:

- CHD
 - Acute myocardial infarction
 - Silent myocardial infarction
 - Unstable angina
 - Coronary revascularization procedure
 - Other clinically significant CHD diagnosed by invasive or non-invasive testing
- Non-CHD Cardiovascular disease
 - Ischemic stroke
 - Peripheral arterial disease

- Abdominal aortic aneurysm
- Atherosclerotic renal artery stenosis
- Carotid artery disease
- Other risk factors
 - Moderate chronic kidney disease (as defined in protocol)
 - Type 1 or type 2 diabetes mellitus.
 - Calculated 10-year fatal Cardiovascular disease risk SCORE $\geq 5\%$
- Patient's history of allergies (described using all pre-printed terms collected in the medical allergic history e-CRF page)

Medical or surgical history will be based on items or combination of items pre-listed in the dedicated medical history e-CRF page (unless otherwise specified).

All medical history information pre-listed or not in the e-CRF, will be coded using the version of Medical Dictionary for Regulatory Activities (MedDRA) currently in effect at Sanofi at the time of database lock.

Disease characteristics at baseline

Specific disease characteristics include:

- Type of hypercholesterolemia
 - heFH
 - Non-familial hypercholesterolemia
- For heFH patients
 - Time from diagnosis of heFH (years)
 - Confirmation of diagnosis (genotyping (Yes, No), clinical criteria (Yes, No))
- For Non-familial hypercholesterolemia patients:
 - Time from diagnosis of hypercholesterolemia (years)
- Background LMT at randomization as reported in dedicated prior and concomitant medications e-CRF pages
 - Atorvastatin daily dose in mg (10, 20, 40,80, Other)
 - Rosuvastatin daily dose in mg (5, 10, 20, 40 Other)
 - Other statins (if any)
 - Any LMT other than statins
 - Any LMT other than nutraceuticals (by therapeutic class and drug name)

- Nutraceuticals (Omega 3 Fatty Acids, Plantago Seed, Phytosterol, Other Nutraceutical)

Other baseline characteristics

Other baseline characteristics include body mass index in kg/m² (quantitative and qualitative variable: <30, ≥30), alcohol habits.

Lipid parameters (quantitative variables for all parameters and the following qualitative variable) will be also summarized at baseline (definitions in [Section 2.1.3](#)):

- Calculated LDL-C: <70, ≥70 to <100, ≥100 to <130, ≥130 to <160, ≥160 to <190, ≥190 mg/dL, ie, <1.81, ≥1.81 to <2.59, ≥2.59 to <3.37, ≥3.37 to <4.14, ≥4.14 to <4.91, ≥4.91 mmol/L

Any technical details related to computation, dates and imputation for missing data are described in [Section 2.5.3](#).

2.1.2 Prior or concomitant medications

All medications will be coded using the World Health Organization-Drug Dictionary using the versions currently in effect at Sanofi at the time of database lock.

- Prior medications are those the patient used prior to first IMP intake. Prior medications can be discontinued before first dosing or can be ongoing during treatment phase.
- Concomitant medications during the parallel-arm period are any treatments received by the patient from first IMP injection to first IMP injection +70 days for patients choosing not to continue into the single-arm period. For patients entering in the single-arm period, concomitant medications will be truncated at the day before second IMP injection.
- Concomitant medications during the single-arm period are defined as any treatments received by the patient from the second IMP injection to the last open-label IMP injection +70 days.
- Post-treatment medications are those the patient took in the period starting from 71 days after the last IMP injection.

2.1.3 Primary endpoint

The primary endpoint is the number (%) and types of SYDNEY-associated PTCs at the unsupervised injections on Weeks 4, 8, and 12. In this study, a PTC is defined as any complaint reported on the Patient Complaint form that triggered an investigation by the Device Department and was classified by this department as device-related, patient-related, or undetermined, whether or not associated with an AE. The complaints categorized as not related to device or patient will not be considered as a PTC. This definition will be used for both primary and secondary endpoints.

2.1.4 Secondary endpoints

2.1.4.1 Device-related endpoints

During the parallel-arm period, patients are to receive injection(s) with either SYDNEY device or current AI. During the single arm period, all patients are to receive 3 separate injections with the SYDNEY device only.

The following endpoints will be analyzed:

- For both devices:
 - Number and percentage of patients with SYDNEY or current AI- associated PTCs (overall and by type) at the supervised injections on Day 1
 - Injection experience questionnaire on Day 1
- For SYDNEY only:
 - Number and percentage of patients with a SYDNEY- associated PTC (overall and by type) at the unsupervised injections on Weeks 4, 8, and 12
 - Patient perspective questionnaire
 - Injection-Treatment Acceptance Questionnaire

2.1.4.2 Pharmacokinetic variables

Concentrations of total alirocumab, total and free PCSK9 in serum are assessed at Day 1, Week 1, Week 2, Week 3, Week 4, Week 8, Week 12, Week 13, Week 14, Week 15 and Week 16.

The PK parameters will include, but may not be limited to C_{max} , t_{max} and AUC_{0-tau}.

2.1.4.3 Anti-drug antibodies variables

ADA will be assessed at baseline (Day 1), Week 4 and Week 16. The following variables will be described:

- ADA response (Positive or Negative). For ADA positive:
 - Titer levels
- Pre-existing positive ADA defined as patients with positive ADA response at baseline with less than 4-fold increase in titer in the post-baseline period

- Treatment-emergent positive ADA response defined as 1) Patients with no ADA positive response at baseline but with any positive response in the post-baseline period or 2) Patients with a positive ADA response at baseline and at least a 4- fold increase in titer in the post-baseline period. For treatment-emergent positive ADA, the following categories for ADA duration will be applied:
 - A persistent positive response is a treatment-emergent ADA positive response detected in at least 2 consecutive post-baseline samples separated by at least a 12-week period
 - An indeterminate duration positive response is defined as ADA present only at the last sampling time point
 - A transient positive response is defined as any treatment-emergent positive ADA response that is neither considered persistent nor indeterminate

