2.4.4.2.2 Pharmacokinetic variables

All analyses for PK variables will be presented by treatment group for the parallel-arms period and overall for the single-arm period.

All the PK analyses will be performed using the PK population in each period.

PK parameters (C_{max} , t_{max} , AUC_{0-tau} and C_{trough}) will be summarized (mean, geometric mean, median, standard deviation, standard error of mean, coefficient of variation, minimum, and maximum).

For the parallel-arms period, log-transformed C_{max} , AUC_{0-tau} and C_{trough} , estimates and 90% CI for the ratio of geometric means (SYDNEY/ AI) will be provided using an ANCOVA model with treatment group (SYDNEY, AI) as fixed effect and baseline body weight as covariate.

2.4.4.2.3 *Anti-drug antibodies variables*

The following summaries will be performed on the ADA population by treatment group for the parallel-arm period and overall for the single-arm period, taking into account all samples regardless of timing in relation to injections:

- ADA results (negative or positive) by time point
- ADA titers using descriptive statistics (median, minimum, and maximum) for positive ADA by time point
- Number (%) of patients with pre-existing ADA and number (%) of patients with treatment emergent ADA positive response
- Number (%) of patients with persistent/indeterminate /transient treatment-emergent ADA positive response
- Time to onset of treatment-emergent ADA positive response using descriptive statistics.

2.4.4.2.4 *Pharmacodynamic variables (lipid variables)*

Continuous endpoints anticipated to have a normal distribution

Continuous variables anticipated to have a normal distribution (ie, percent change in LDL-C, Total-C, HDL-C at Week 4) will be analyzed in the mITT population of the parallel-arm period using an ANCOVA model with fixed categorical effect of treatment group (SYDNEY, AI), as well as the continuous fixed covariate of corresponding baseline value. LS means and 95% CI will be provided for both SYDNEY and AI.

Depending on the number of missing LDL-C values at Week 4, a sensitivity analysis may be performed using multiple imputations (with baseline LDL-C and device group factors included in the imputation model) using the MI SAS® procedure to impute missing data followed by ANCOVA model. Results will be combined using Rubin's formulae with the SAS MIANALYZE procedure.

Continuous endpoints anticipated to have a non-normal distribution

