2.5.4 Windows for time points

Data analyzed by time point (except PK and PCSK9 variables) will be summarized using the analysis windows given in Table 1. These analysis windows will be applicable for all analyses, and they are defined to provide more homogeneous data for time point-specific analyses. For PK, since measurements are planned every week, e-CRF visits will be used instead of analysis windows.

Table 1 - Analysis windows definition

Time point	Targeted study day	Analysis window in study days
Week 4	29	15 to 42
Week 8	57	43 to 70
Week 12	85	71 to 98
Week 16	113	99 to 126

Study days are calculated from the day of first IMP injection, the day of first open-label IMP injection being Day 1. For randomized but not treated patients, Day 1 is the day of randomization.

If multiple valid values of a variable exist within an analysis window, the nearest from the targeted study day will be selected. If the difference is a tie, the value after the targeted study day will be used. If multiple valid values of a variable exist within a same day, then the first value of the day will be selected when time is available, else the scheduled visit will be selected.

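### The 12-week rule for persistent ADA equals the nominal gap between the only two post-baseline samples, and the SAP does not say whether the category is derived per patient or per period, so some patients positive at every post-baseline sample can be labelled transient or indeterminate

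*SAP*

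**What the plan says.** SAP 2.1.4.3 sets the sampling schedule: "ADA will be assessed at baseline (Day 1), Week 4 and Week 16". It then splits treatment-emergent responses into three classes by duration:

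- *Persistent*: "detected in at least 2 consecutive post-baseline samples separated by at least a 12-week period".
- *Indeterminate*: "An indeterminate duration positive response is defined as ADA present only at the last sampling time point".
- *Transient*, the residual class: "A transient positive response is defined as any treatment-emergent positive ADA response that is neither considered persistent nor indeterminate".

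SAP 2.4.4.2.3 plans the output "Number (%) of patients with persistent/indeterminate /transient treatment-emergent ADA positive response". It is to be presented "by treatment group for the parallel-arm period and overall for the single-arm period", "taking into account all samples regardless of timing in relation to injections". SAP 2.3.4 defines a separate ADA population for each period, and each requires a post-baseline sample in that period.

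Neither section says whether the 12 weeks are counted in actual dates or in nominal time points. Neither says whether the class is derived from all of a patient's samples or only from those within a period. The protocol (11.4.5) leaves ADA detail to the SAP.

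**The concern.** The threshold for *persistent* is the same length as the scheduled gap between the only two samples that can establish it. Any shortening of that gap removes the patient from *persistent*. A patient who was also positive at Week 4 is not *indeterminate* either, because ADA was not present only at the last sample. The residual rule then assigns *transient*. To a reader that label means the antibody went away, yet this patient has no negative post-baseline sample.

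If the table is instead built within each period, each period has one scheduled post-baseline sample, and the two-sample criterion cannot be met.

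At stake is a planned secondary immunogenicity table. In these cases the label reflects visit timing, early discontinuation or a programming choice rather than the antibody result.

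**Working it through.** The documents give no ADA rate and no expected count per class, so there is no plan figure to reproduce.

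**Inputs**
- Post-baseline ADA samples: Week 4 and Week 16 (SAP 2.1.4.3), on Day 29 ± 3 and Day 113 ± 3 (Protocol 1.2). The Week 4 sample is drawn before dosing.
- Table 1 windows (SAP 2.5.4): Week 4 = Days 15–42, Week 8 = 43–70, Week 12 = 71–98, Week 16 = 99–126.
- Early last samples: a final visit four weeks after premature discontinuation (Protocol 10.3.4), or end-of-study procedures at withdrawal if possible (Protocol 10.3.5). End-of-study procedures include ADA (Protocol 10.1.8).
- 66 randomized and 60 evaluable patients (Protocol 11.1).
- Assumptions: 1% to 10% of patients positive at both post-baseline samples; visit deviations independent.

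**Step 1. Scheduled gap.** 113 − 29 = 84 days = 12 × 7. In-window extremes are 110 − 32 = 78 and 116 − 26 = 90 days.

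**Step 2. Completers positive at both visits, samples pooled across periods.**
- *Actual dates.* There are 7 × 7 = 49 day pairs. The gap is under 84 days when the Week 16 deviation is smaller than the Week 4 deviation: (49 − 7)/2 = 21 pairs, or 43% if all days are equally likely. If 90% of visits are on target and the rest are spread evenly over ±1 to ±3 days, the share is (1 − [0.9² + 6 × (0.1/6)²])/2 = (1 − 0.8117)/2 = 9.4%. If all visits are on target it is 0.
- Both-positive patients number 66 × 0.01 to 0.10 = 0.66 to 6.6. Relabelled *transient*: 0.06 to 0.62 patients at 9.4%, and 0.28 to 2.83 in the uniform case.
- *Table 1 time points.* All 49 pairs are Week 4 and Week 16, 12 weeks apart. Nobody is relabelled.

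**Step 3. Early last sample, samples pooled across periods.** With a last sample on Day 98 at the latest, the largest date gap is 98 − 15 = 83 days (98 − 26 = 72 with Week 4 inside its visit window). By Table 1 label the gap is 4 or 8 weeks. Crossing Days 15–42 with Days 43–98 gives 28 × 56 = 1,568 combinations, and none is *persistent* on either basis. With Week 4 positive, all are *transient*.

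| Discontinuation | Final visit (+28 days) | Table 1 label | Gap from Day 29 | Label gap |
|---|---|---|---|---|
| Day 29–42 | Day 57–70 | Week 8 | 28–41 days | 4 weeks |
| Day 43–70 | Day 71–98 | Week 12 | 42–69 days | 8 weeks |
| Day 71–84 | Day 99–112 | Week 16 | 70–83 days | 12 weeks |

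The last row is *persistent* on Table 1 time points and *transient* on dates.

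Upper-end size: planned drop-out is 66 − 60 = 6 patients. Suppose all 6 stop evenly over Days 29–84, attend the early final visit and give no later sample. Then (14 + 28)/56 = 75%, or 4.5 patients, have a last sample before Day 99. At 1% to 10% both-positive that is 0.045 to 0.45 patients. It is 0 if all of them give a Week 16 sample.

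**Step 4. Category derived within each period.** Taking the pre-dose Week 4 sample as part of the parallel-arm period, that period has one scheduled post-baseline sample. The single-arm period also has one (Week 16, or the early final visit). Two consecutive positives cannot occur on scheduled samples, so the *persistent* row is empty by construction. A patient positive at both visits is *indeterminate* in each period. The exception is a patient who never takes the second injection: both samples then fall in the parallel-arm period, and Step 3 applies.

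**The case against.** Four points on the other side deserve weight.

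1. **Table 1 largely settles the interval basis.** SAP 2.5.4 says "These analysis windows will be applicable for all analyses" and exempts only PK and PCSK9. ADA is scheduled by named time point, and Week 4 to Week 16 is exactly 12 weeks, so the rule fits a nominal reading. This mostly stands. What is left is that 2.1.4.3 speaks of samples separated by a period and does not say that the window label measures it. Table 1 does not help the early last sample.

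2. **Early last samples may be rare.** Protocol 10.3.4 also calls for follow-up to the scheduled completion date, and a Week 16 sample removes the problem. A drop-out with no sample after Week 4 is *indeterminate* under the present rule. The 10% drop-out figure gives neither timing nor sampling. This stands, so 4.5 patients is an upper-end assumption, not an expectation.

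3. **The by-period table changes the label.** A reader might infer that a patient positive at Week 4 and at an early last sample is *transient* however the table is programmed. The documents do not support that. It requires pooling across periods, or a patient without a second injection. The within-period reading is no better, since it empties the *persistent* class.

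4. **A residual class is a legitimate convention.** The three classes are exhaustive and do not contradict each other. That is so, but it does not make *transient* a fair description of a patient who was never negative after baseline.

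**Conclusion.** The point holds as a minor defect of definition. The SAP leaves two derivations open, and both misdescribe patients positive at every post-baseline sample. Pooled across periods, those with a last sample before Day 99 become *transient*, as do completers with a 78- to 83-day gap if actual dates are used. Derived within periods, *persistent* cannot occur on scheduled samples.

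The number mislabelled *transient* is probably a fraction of one patient. That rests on the assumed 1% to 10% both-positive rate and on assumed visit adherence, drop-out timing and final sampling. Only the combination of 10% positivity with visits uniform over ±3 days, counted on actual dates, reaches 2.8 patients. On the within-period reading the both-positive patients (0.66 to 6.6 under the same assumption) appear as *indeterminate*, not *transient*.

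A reader might also infer that 43% of both-positive completers will be mislabelled, or that the immunogenicity results as a whole are unsafe. Neither follows. The 43% needs both actual dates and uniform visit days, and Table 1 points away from actual dates. Treatment-emergent ADA counts, titers, results by time point and the primary endpoint do not use the duration classes.

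**What to change.** Before database lock, amend SAP 2.1.4.3 and add one sentence to 2.4.4.2.3:

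- Derive the duration category once per patient from all post-baseline samples across both periods.
- *Persistent*: treatment-emergent ADA positive at both the Week 4 and Week 16 time points, assigned by Table 1, and at any sample between them. The last clause covers unscheduled ADA samples taken after certain allergic events (Protocol 10.6.2.1), which could otherwise break up the pair of consecutive samples.
- *Indeterminate*: positive at the last available sample but not *persistent*.
- *Transient*: negative at the last available sample.

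Do not use the e-CRF visit label to assign ADA samples. An early final visit recorded as Week 16 could then count as *persistent* with a gap as short as 28 days from Day 29.

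The cost is a short change to the SAP text, with no new samples or visits and no change to 2.5.4. The downside is that *persistent* then rests on time points, so the actual gap may be under 12 weeks: 78 to 90 days for visits in window, and 99 − 42 = 57 to 126 − 15 = 111 days at the limits of Table 1.
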